4 ELIGIBILITY

4.1 Inclusion Criteria

1. Age ≥ 18 years old
2. HIV1 or HIV2, regardless of CD4 cell count
3. HIV Viral load <200 copies/mL
4. Proven histologically and/or cytologically, stage IIIB-IV or metastatic relapse post-surgery non-small cell lung cancer (NSCLC)
5. Disease recurrence or progression during/after at least one prior platinum doublet-based chemotherapy regimen for advanced or metastatic disease
6. Measurable disease by Computed tomography (CT)/Magnetic resonance imaging (MRI) per RECIST 1.1 criteria
7. Performance status (PS) 0, 1 or 2
8. Written informed consent
9. Patients must have adequate organ function: creatinine clearance > 40 mL/min (Cockcroft, MDRD or CKD-Epi formula or 24h Urine Calculate creatinine clearance from a 24h urine collection), neutrophiles count > 1500/mm³; platelets > 100 000/mm³ ; hemoglobine > 9 g/dL; hepatic enzymes < 3N with total bilirubin ≤ 1.5 × ULN (upper limit of normal) except subjects with documented Gilbert's syndrome (≤ 5 × ULN) or liver metastasis, who must have a baseline total bilirubin ≤ 3.0 mg/dL
10. Patients must receive appropriate care and treatment for HIV infection including ART when clinically indicated and subjects should be under the care of a physician experienced in HIV management. In case of recent introduction of cART and CD4 levels <50 cells/ml, inclusion will be possible provided subjects had at least 4 weeks of

treatment prior to inclusion, to avoid clinical type IRIS (immune inflammatory syndrome reconstitution). All antiretroviral treatments are allowed.

11. Females of childbearing potential who are sexually active with a nonsterilized male partner must use a highly effective method of contraception for 28 days prior to the first dose of investigational product, and must agree to continue using such precautions for 6 months after the final dose of investigational product; cessation of contraception after this point should be discussed with the referent physician. Periodic abstinence, the rhythm method, and the withdrawal method are not acceptable methods of contraception. They must also refrain from egg cell donation for 6 months after the final dose of investigational product. Men receiving nivolumab and who are sexually active with women of childbearing potential will be instructed to adhere to contraception (appendix I) for a period of 31 weeks after the last dose of nivolumab.
12. Persons deprived of liberty could be eligible because the expected benefice (improvement of disease control rate) justifies the foreseeable risk (adverse reaction of nivolumab).

4.2 Exclusion Criteria:

1. Concurrent malignancies requiring active intervention
2. Active Infection
3. Patient with known EGFR activating tumor mutation or known ALK or ROS1 gene rearrangement not treated with the appropriate targeted therapy.
4. History of immunological events related to HIV: lymphoid interstitial pneumonitis (LIP), non-infectious uveitis, encephalitis and other manifestations of CD8 lymphocyte infiltration syndrome, HIV-associated nephropathy (HIVAN).
5. Subjects with active, known or suspected autoimmune disease. Subjects with vitiligo, type I diabetes mellitus, residual hypothyroidism due to autoimmune thyroiditis only requiring hormone replacement, or conditions not expected to recur in the absence of an external trigger are permitted to enroll.
6. Active or history of inflammatory bowel disease (eg, diverticulitis, colitis, Crohn's, coeliac disease or other serious gastrointestinal chronic conditions associated with diarrhea). Note that diverticulosis is permitted.

7. Symptomatic cerebral metastasis unless treated by brain radiotherapy which will be completed for at least 15 days before the beginning of the treatment; subjects with carcinomatous meningitis.
8. Prior treatment with an anti-PD-1, anti-PD-L1, anti-PD-L2, anti-CTLA-4 antibody, or any other antibody or drug specifically targeting T-cell co-stimulation or checkpoint pathways.
9. The last dose of prior chemotherapy or radiation therapy (with the exception of palliative radiotherapy) was received less than 3 weeks prior to inclusion;
10. History of primary immunodeficiency, history of organ transplant that requires therapeutic immunosuppression and the use of immunosuppressive agents within 28 days of inclusion or a prior history of severe (grade 3 or 4) immune mediated toxicity from other immune therapy.
11. Subjects with a condition requiring systemic treatment with either corticosteroids (> 10 mg daily prednisone equivalent) or other immunosuppressive medications within 14 days of inclusion. Intranasal/inhaled or topical steroids, and adrenal replacement steroid doses \leq 10 mg daily prednisone equivalent, are permitted in the absence of active autoimmune disease.
12. Female subjects who are pregnant, breast-feeding or male or female patients of reproductive potential who are not employing an effective method of birth control.
13. Legally protected adults.

5 Concomitant treatment

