13.5 Data Monitoring Committee

A Data Monitoring Committee (DMC) will be utilized to provide general oversight and safety considerations for this study. The DMC will provide advice to the Sponsor regarding actions the committee deems necessary for the continuing protection of subjects enrolled in this study. The DMC will be charged with assessing such actions in light of an acceptable risk/benefit profile for nivolumab. The DMC will act in an advisory capacity to IFCT and will monitor subject safety data for the study.

The DMC will be advisory to the clinical study leadership team. The clinical study leadership will have responsibility for overall conduct of the study including managing the communication of study data.

The Intergroup will be responsible for promptly reviewing the DMC recommendations, for providing guidance regarding the continuation or termination of the study, and for determining whether amendments to the protocol or changes to the study conduct are required.

A safety run will be done after the first 5 patients then every 10 patients (8 weeks follow up) and will be reviewed by the DMC in attempt to detect unexpected immunovirologic side effects, ie increase in HIV viral load, decrease of CD4 cell count or unexpected high frequency of IRIS.

Details of the DMC responsibilities and procedures will be specified in the DMC charter.

The DMC recommendations will be sent to ANSM for information.

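### The CD4 limit that triggers the four-week antiretroviral condition is written per millilitre, so as written the rule covers practically no one

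*Protocol*

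**What the plan says.** All the entry rules that matter here stand in Protocol section 4.1.

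- **Criterion 2** admits patients with "HIV1 or HIV2, regardless of CD4 cell count", so there is no general CD4 floor.
- **Criterion 9** sets organ-function limits and gives both of its blood cell counts per mm³: "neutrophiles count > 1500/mm³" and "platelets > 100 000/mm³".
- **Criterion 10** deals with HIV care. It contains the one CD4-dependent condition: "In case of recent introduction of cART and CD4 levels <50 cells/ml", "inclusion will be possible provided subjects had at least 4 weeks of" treatment before inclusion. The sentence gives its own reason, which is to avoid clinical IRIS.

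The protocol gives no other numeric CD4 threshold, does not restate the rule elsewhere and offers no conversion. Section 13.5 asks the DMC to look for, among other things, an "unexpected high frequency of IRIS".

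**The concern.** The CD4 limit in criterion 10 uses a different volume unit from the cell counts in the line above it, and the two units differ by a factor of 1000. Read literally, the clause describes a group that hardly exists, so it cannot do what it says it is for. This is an operative eligibility rule with a safety motive, not background text.

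Two things are at stake. First, a patient who has recently started antiretrovirals and has a very low CD4 count could enter before four weeks of treatment and still comply with the text. Second, section 3 plans twenty centres. If each settles the unit for itself, the same patient could be eligible at one site and not at another, and a monitor would have no text to decide between them.

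**Working it through.** The threshold is a stated cut-off with no formula behind it, so there is no planned figure to reproduce. The check is a unit conversion followed by a reading of which counts meet the condition.

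**Inputs (all Protocol section 4.1)**
- CD4 limit: below 50 cells per mL (criterion 10)
- Neutrophil limit: above 1500 per mm³ (criterion 9)
- Platelet limit: above 100 000 per mm³ (criterion 9)
- Conversion: 1 mL = 1000 mm³

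**Step 1. Put the CD4 limit in the unit of criterion 9.**
50 cells/mL ÷ 1000 mm³/mL = 0.05 cells/mm³.

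**Step 2. Size of the unit gap.**
The figure 50 taken per mm³ would be 50 × 1000 = 50 000 cells/mL. The ratio of the two readings is 50 000 / 50 = 1000.

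**Step 3. Which counts meet the condition as written?** Multiply a count per mm³ by 1000 and compare it with 50.

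| CD4 per mm³ | CD4 per mL | Below 50 per mL? |
|---|---|---|
| 0 | 0 | yes |
| 1 | 1000 | no |
| 5 | 5000 | no |
| 10 | 10 000 | no |
| 25 | 25 000 | no |
| 49 | 49 000 | no |

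A count of 1 cell/mm³ is already 1000 / 50 = 20 times the limit. Among whole-number counts per mm³, only a reported 0 triggers the rule.

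**Step 4. Comparison within the list.**
The neutrophil limit is 1500 × 1000 = 1 500 000 per mL, which is 1 500 000 / 50 = 30 000 times the CD4 limit as written. If both were per mm³ the ratio would be 1500 / 50 = 30. This shows how far the CD4 figure stands from its neighbours. It does not establish the intended value.

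**Step 5. Effect on the design.**
The CD4 limit does not enter the hypotheses, error rates or decision rule in section 13.2, so alpha, power and sample size do not change.

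**The case against.** **The unit may be a reading artefact.** Criterion 10 has a lower-case ml where the same list otherwise writes mL, and section 14.1 gives slide thicknesses as 20m and 4x10m, where a micro sign has evidently been lost. If a micro sign had been turned into an m, cells per microlitre would appear as cells/ml. However, the same sentence in section 14.1 also lacks an accented letter in a hospital name, which suggests that special characters were dropped rather than replaced. A dropped sign in criterion 10 would leave cells/l, not cells/ml. An artefact is therefore possible but not shown, and the sponsor can settle it from the source file.

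**A reader might infer that the IRIS safeguard never applies.** That goes too far. A reported count of 0 would still trigger it. The sentence also states its purpose, and criterion 10 calls for care by a physician experienced in HIV, who would probably not take the limit to be 0.05 cells/mm³. This lowers the practical harm, but leaves a rule that works only if sites depart from its wording.

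**A reader might infer that patients have no other protection at entry.** The protocol does not support this. Criterion 3 requires a viral load below 200 copies/mL, criterion 10 requires experienced HIV care, exclusion 2 removes active infection, and exclusion 4 removes a history of HIV-related immunological events. After entry, CD4 and viral load are measured before each infusion (section 8.1), and the DMC reviews safety after the first 5 patients and then every 10 (section 13.5). These conditions stand as partial protection, but none of them sets a minimum time on antiretrovirals.

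**A reader might infer that the primary analysis is compromised.** Section 13.4.1 analyses eligible patients, and section 13.3 defines these by the absence of major deviations from the entry criteria, so a link exists in principle. It remains speculative. Deviations are reviewed and classed as minor or major, an ITT sensitivity analysis is planned, and a patient would have to combine recent treatment, a very low CD4 count, a viral load already below 200 and less than four weeks on treatment. The protocol gives no number for such patients among the 30 planned.

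**The intended unit is inferred.** Neutrophils and platelets are different cells, and the CD4 limit is stated only once. This stands, and it is why the remedy asks for confirmation and does not supply a value.

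**Conclusion.** Wrong as written; minor severity. The limit in criterion 10 equals 0.05 cells/mm³, a factor of 1000 away from the same figure in the unit used for the other blood cell counts in the list. The only entry rule expressly aimed at IRIS therefore reaches practically no one on its literal terms, and its practical effect depends on how each site reads the unit.

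This rests on the text as it stands being the text the sponsor approved, and on CD4 counts being reported as whole numbers per mm³ for the statement that only 0 qualifies. The document does not say how many patients the rule was meant to cover, so the number affected cannot be given. Nor does it show what value was meant, and this point takes no position on that.

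**What to change.** 1. Check criterion 10 against the source file to exclude a lost or altered character.
2. Confirm the intended CD4 threshold together with its unit, and reconcile criterion 10 with the units used in criterion 9.
3. Carry the same wording into the eligibility checklist, so that every site and the review of deviations under section 13.3 apply one rule.

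The threshold and the length of the lead-in remain the sponsor's decision. The cost is one clarified unit in an amendment and in the checklist, with no change to the design or the analysis.

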5.1 Authorized concomitant treatment

Subjects are permitted the use of topical, ocular, intra-articular, intranasal, corticosteroids (with minimal systemic absorption). Adrenal replacement steroids dosed $<$ 10 mg daily prednisone are permitted. A brief (less than 3 weeks) course of corticosteroids \geq for prophylaxis (eg, contrast dye allergy) or for treatment of non-autoimmune conditions is permitted.

Concomitant palliative and supportive care for disease related symptoms is allowed if initiated prior to first dose of study therapy. Prior palliative radiotherapy must have been completed at least 2 weeks prior to inclusion.

5.2 Prohibited concomitant treatment

The following medications are prohibited during the study (unless required to treat a drug related adverse event):

- Immunosuppressive agents
- Immunosuppressive doses of systemic corticosteroids (>3 weeks of prednisone 10 mg per day or equivalent dose if administration of another corticosteroid)
- Any concurrent anti-neoplastic therapy (ie chemotherapy, hormonal therapy, immunotherapy, extensive, non-palliative radiation therapy, or standard or investigational agents for treatment of lung cancer)

6 Criteria for early termination, withdrawal from the trial or study termination

6.1 Withdrawal from the trial

Reasons for withdrawal from the trial are:

- Patient withdraws consent
- Death

Patients have the right to withdraw their consent and request to leave the study at any time for any reason (which they are not obligated to explain). This should not affect their right to future care.

6.2 Early treatment termination

The investigator may terminate a patient's participation early in the event of:

- Tumour progression during treatment
- Toxicity requiring termination of study treatments
- Intercurrent illness
- Protocol violation
- Non-compliance (nivolumab)
- Administrative reasons
- Pregnancy

7 PRE-TREATMENT EVALUATION:

Investigations		Timing
History and Physical Exam including:	
 history including (occupational), smoking history physical examination including height, weight, pulse, blood pressure performance status (PS) 	Within 14 days of inclusion
Haematology	
 CBC including haemoglobin, differential, platelet count 	Within 14 days of inclusion
Biochemistry	
 AST (SGOT) and ALT (SGPT) alkaline phosphatase bilirubin albumin serum creatinine lipase fasting glucose K, Cl, Na, Mg, Ca, P LDH CRP TSH (T3, T4 if TSH abnormal) INR/APTT 	Within 14 days of inclusion
Immunovirology	
 Serology EBV, HCV/HBV, CMV, Toxoplasmosis - TPHA-VDRL, HHV-8 Quantiferon 	Before inclusion
	
 CD4/CD8 cell counts HIV viral load (VL) HCV/HBV VL, HHV-8 VL in the case of co-infection EBV VL, CMV VL 	Within 28 days of inclusion ; those VL will be monitored further in case of positivity
Radiology ¹	
 baseline CT brain, chest and abdomen (with iodine injection) (Wang 2004) baseline PET-CT : highly recommended (but optional) (Ceresoli 2006b, von Schulthess 2006, Francis 2007) 	Within 28 days of inclusion
	
 other baseline imaging (e.g. bone scan,...) 	Required, within 28 days of inclusion, only if suspicious signs/symptoms are present
Correlatives	
 tumour tissue for assessment of PD-L1 status 	From initial diagnosis block

	
 whole blood, serum, plasma for correlatives 	Prior to cycle 1, day 1 dosing
Other Investigations	
 ECG 	Within 14 days of inclusion
	
 pregnancy test if applicable 	Within 24hrs of first drug administration
Adverse Event	Baseline adverse event evaluation (to document residual adverse event from previous therapy and baseline symptoms)	Within 14 days of inclusion
Quality of Life	LCSS questionnaire	Within 14 days of inclusion

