3 REGIMEN

Thirty eligible patients, previously treated by at least one line of platinum-based chemotherapy, will be included.

[figure not shown]
TREATMENT:

Nivolumab is administered intravenously (IV), over 30 minutes at 3 mg/kg every 2 weeks, until disease progression, death, limiting toxicity or patient refusal.

Premedication is not required.

Patients with tumoral progression will stop the treatment but will have a follow-up for the secondary endpoints of OS, and the toxicities assessment till a last study visit 4 weeks (\pm 1 week) after the last injection of the drug.

Twenty centers will be opened.

Schedule of the study design.

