8.2 Evaluation after protocol treatment

	Investigations	Timing
History and Physical Exam including:	
 physical examination including, pulse, blood pressure, weight performance status 	Within 30 days following last treatment day
Hematology	
 CBC including haemoglobin, differential, platelet count 	Within 30 days following last treatment day
Biochemistry	
 AST (SGOT) and ALT (SGPT) alkaline phosphatase bilirubin albumin creatinine lipase (and amylase if abnormal lipase) fasting glucose K, Cl, Na, Ca 	Within 30 days following last treatment day
	
 TSH (T3, T4 if TSH abnormal) 	As clinically indicated
Radiology*	
 CT-scan of chest and upper abdomen 	Every 8 weeks
Other	
 ECG 	As clinically indicated

Investigations	
• lung function tests: FEV1, FVC, TLCO and blood gas at room atmosphere	As clinically indicated
Adverse Events	Patients must be evaluated for treatment related adverse events until resolution	

* Only for patients who have not yet discontinued the study treatment

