13.4.2 Secondary endpoints

- Progression-free Survival (PFS) and Overall Survival (OS)

PFS is defined as the time between the date of inclusion and the first date of documented progression or death due to any cause, whichever occurs first. Subjects who die without a reported progression will be considered to have progressed on the date of their death. Subjects who did not progress or die will be censored on the date of their last evaluable tumor assessment.

The duration of overall survival is defined as the time elapsed between the date of inclusion and death. Subjects who did not die will be censored on the last date a subject was known to be alive.

The median survival, 95% confidence intervals and an estimation of progression-free survival (PFS) and overall survival according to the Kaplan-Meier Method will be calculated using standard methods

This analysis will be performed on all eligible patients.

PFS and OS will be also conducted on all patients (ITT analysis) as a sensitivity analysis.

- Tolerance

The toxicity analysis will be performed on the safety population.

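### Section 6.2 ends a patient's participation where it should end treatment only, and section 8.2 schedules no survival contact and, read literally, no scans after treatment stops, which leaves OS and PFS open to informative censoring

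*Protocol*

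**What the plan says.** Section 6 separates two events. For leaving the trial, section 6.1 ("Reasons for withdrawal from the trial are") gives only consent withdrawal and death. The next section is headed "6.2 Early treatment termination", but its operative sentence is "The investigator may terminate a patient's participation early in the event of" a list of reasons: progression, toxicity, intercurrent illness, protocol violation, non-compliance, administrative reasons and pregnancy.

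Section 3 says: "Patients with tumoral progression will stop the treatment but will have a follow-up for the secondary endpoints of OS". The sentence continues "and the toxicities assessment till a last study visit 4 weeks" after the last injection. It concerns progressors only.

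In the section 8.2 table, the examination and routine laboratory rows are due once, "Within 30 days following last treatment day". Chest and upper-abdomen CT is listed every 8 weeks, with the footnote "Only for patients who have not yet discontinued the study treatment". Treatment-related adverse events are followed to resolution. There is no vital-status row.

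For OS, section 13.4.2 states: "Subjects who did not die will be censored on the last date a subject was known to be alive". For PFS, it censors patients without progression or death at their last evaluable tumour assessment.

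**The concern.** A site that follows 6.2 to the letter may release a patient whom 6.1 and section 3 keep on study. Kaplan-Meier estimation assumes that censored patients have the same outlook as those still followed. Censoring linked to progression or toxicity can break that assumption. No analysis plan can recover vital status or scans that were never collected, so the protocol itself has to settle who is followed, for what and until when.

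OS and PFS are both secondary endpoints of a single-arm trial. There is no control arm in which the same follow-up practice would operate, so any distortion goes straight into the reported medians.

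**Working it through.** **1. Follow-up by reason for stopping.** The protocol states no figure for OS or PFS, so there is none to reproduce. The provisions compare as follows.

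| Reason for stopping | 6.1 | 6.2 | OS follow-up stated? | Scheduled CT after stopping (8.2) |
|---|---|---|---|---|
| Progression | stays in trial | participation may end | yes, section 3 | none, by the footnote |
| Toxicity, intercurrent illness, violation, non-compliance, administrative, pregnancy | stays in trial | participation may end | no sentence | none, by the footnote |
| Consent withdrawn | leaves | not listed | not applicable | not applicable |

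Sections 6.1 and 6.2 conflict in the first two rows. Section 3 resolves OS for progressors only. No section gives an interval for survival contact in any row. Other sections also presuppose continued participation: 11.3 and 11.4 follow adverse events after treatment, and 11.6 follows a pregnancy to neonatal outcome.

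**2. Consequence for PFS.** The patient affected is one who stops without progression. The footnote removes the 8-weekly scan, and 13.4.2 then censors at the last evaluable scan. A later progression goes unseen unless it is found outside the schedule, and a later death counts only if vital status is known. If stopping treatment goes with a higher risk of progression, PFS is overestimated. If not, precision is lost. No calculation was made for PFS.

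**3. Consequence for OS if some progressors are lost despite section 3.** None of these inputs is in the protocol; all are assumptions:
- exponential time to progression, median 2, 3 or 4 months
- death hazard before progression, 0.03 per month
- exponential survival after progression, median 4 or 8 months
- administrative censoring, uniform between 12 and 54 months

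Survival time is the time of death if death precedes progression; otherwise it is the progression time plus the post-progression time. A random 25% of progressors are censored either 1 month or 100 days after progression, with progression standing in for the last dose. Each scenario has 200,000 simulated patients. Shift = Kaplan-Meier median minus true median, in months.

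| Median to progression / after progression | True median OS | 25% censored at 1 month (shift) | 25% censored at 100 days (shift) |
|---|---|---|---|
| 2 / 4 | 6.4 | 6.6 (0.2) | 6.4 (0.0) |
| 2 / 8 | 10.0 | 10.2 (0.2) | 10.1 (0.1) |
| 3 / 4 | 7.3 | 7.6 (0.3) | 7.4 (0.1) |
| 3 / 8 | 10.7 | 11.1 (0.4) | 10.9 (0.2) |
| 4 / 4 | 8.1 | 8.5 (0.4) | 8.2 (0.1) |
| 4 / 8 | 11.6 | 12.0 (0.4) | 11.8 (0.2) |

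The shift is 0.2-0.4 months at 1 month and 0.0-0.2 months at 100 days.

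**4. Consequence for OS if patients who stop without progression are lost.** This is the group with no stated OS follow-up. The assumptions are similar: median time to progression 2.5-3.5 months, death hazard 0.03-0.05 per month, post-progression median 4-8 months. If 8-21% of patients stop before progression, are censored 1 month later and have the same prognosis as the rest, the Kaplan-Meier median moves by 0.0 to -0.2 months. It falls slightly because patients who have not yet progressed leave the risk set. A worse prognosis in those who stop would push it the other way, so even the direction is uncertain for this group.

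**The case against.** The strongest reply is that this is loose drafting under a clear heading. Section 6.2 is titled as treatment termination, 6.1 separately limits withdrawal from the trial, and section 3 promises OS follow-up to progressors, likely the largest group. The CT footnote sits in a table for the period after treatment, where it would apply to almost nobody, so it is probably a slip. Much of this stands: the intended meaning can be guessed. But a site works from the operative sentence and the visit table, and neither says what the heading implies. For patients who stop without progression, there is no other sentence to fall back on for OS.

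A reader might go further and infer that OS will be censored about a month after the last dose in essentially all patients, with a large inflation of the median. The documents do not support that. Section 3 keeps progressors under OS follow-up, and its 4-week limit attaches most naturally to the toxicity assessment. Section 11.3 collects adverse events to 100 days and related events beyond that. Section 11.4 follows adverse events past the observation period. Section 15.6 keeps the study open until one year after the last patient's last treatment. Section 13.4.2 censors at the last date known alive, not at the last visit in the 8.2 table.

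It is also fair to say that the trial's decision does not rest on OS or PFS. It rests on disease control at 8 weeks, and section 13.4.1 counts patients who cannot be evaluated as failures.

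**Conclusion.** The point holds as a contradiction that must be reconciled. Section 6.2 conflicts with 6.1 and section 3. OS follow-up is unstated for patients who stop for a reason other than progression. No survival contact is scheduled for anyone, and the CT footnote as written ends scheduled imaging when treatment stops. Followed literally, these provisions allow informative censoring of OS and PFS.

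The size cannot be known from the protocol. It is small if only a minority are lost: about 0.2-0.4 months in median OS with 25% of progressors censored at 1 month, on assumed inputs. If section 3's follow-up is carried out for every patient, the OS bias disappears. The primary 8-week disease control rate is unaffected. The correction is worth making because it is cheap and the missing data could not be recovered later.

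**What to change.** Four wording changes:

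1. In 6.2, replace the phrase about ending participation early with one that says study treatment is stopped early.
2. State that a patient stopped for any 6.2 reason stays on study for vital status and safety unless consent is withdrawn under 6.1.
3. Add a vital-status row to the 8.2 table for all patients, with a stated interval, until the study end in 15.6. The existing 8-week interval would serve.
4. Reword the CT footnote so that patients who stop treatment without progression keep the 8-weekly tumour assessment until progression.

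The cost is brief vital-status checks in at most 30 patients and continued scheduled scans in the few who stop without progression. No dose, treatment rule, sample size or primary analysis changes.
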